1.3 Format and scale of the data

Approximately 20 creatinine readings per study participant captured in encrypted electronic form. Baseline data capture in paper workbook and consolidated into excel workbook

Participant feedback from paper-based questionnaires.

Approximately 72 participants to be recruited (30 will be randomised in to the non-device group therefore will not be sending in creatinine readings)

2. Data collection / generation

2.1 Methodologies for data collection / generation

atinine measurements will be collected by study participants using a point of care creatinine device in home. These measurements will be transferred to a secure Microsoft Azure environment. er data capture in paper workbook and consolidated into excel workbook

2.2 Data quality and standards

icipant measured creatinine readings will be compared with the data downloaded directly from the t of care analyser to assess the accuracy of reporting. each device will be calibrated by the study icipant prior to use and has been calibrated with the hospital laboratory.

3. Data management, documentation and curation

3.1 Managing, storing and curating data.

obile application will be used to capture creatinine readings from a point of care device to storage in osoft Azure environment. These data files are backed up and data is retained or the duration of the ly.

3.2 Metadata standards and data documentation

aim of the study is to publish the results of the study, this would include summary data

3.3 Data preservation strategy and standards

nymised data will be archived with associated meta data

4. Data security and confidentiality of potentially disclosive information

4.1 Formal information/data security standards

Digital Experimental Cancer Medicines Team have an information security policy that will be wed.

4.2 Main risks to data security

Data Collection:

Participant identification from collected data - the unique participant ID used in the study is pseudonymised and no identifiable data is collected. Likelihood of risk occurring is low Participant identification by the creatinine images sent in if they contain personal identifiable information in error - all images will be reviewed by the study team and any image that is at risk of identify the patient will be deleted. Patients will receive training on how to use the app and specifically how to take an image of the creatine device. Likelihood of risk occurring is low

Data Access:

Data is transmitted and stored in encrypted form. Access to the data is controlled and can only be authorised by the study data manager.

5. Data sharing and access

5.1 Suitability for sharing

The purpose of this research and the consent obtained extends only to establishing that the device can be used effectively for home-based creatine readings. Data will be pseudonymised during the study. At the end of the study the data will be anonymised to enable data sharing and protection of patient privacy.

5.2 Discovery by potential users of the research data

The results of the work will be published in Open Access journals

5.3 Governance of access

The Sponsor is the Data Controller and makes all decisions on data sharing

5.4 The study team's exclusive use of the data

There is no exclusivity by the study team over this data. Requests for sharing within the participant consent agreement will be considered by the Sponsor

5.5 Restrictions or delays to sharing, with planned actions to limit such restrictions Requests for sharing within the patient consent agreement will be considered by the Sponsor

5.6 Regulation of responsibilities of users

Access will be considered for external users to anonymized data under a data agreement that ensures compliance with the original patient consent agreements

6. Responsibilities

The Sponsor is accountable for the information in this study. The Sponsor may delegate information control responsibility to the Chief Investigator

7. Relevant institutional, departmental or study policies on data sharing and data security

PolicyURL or Reference

Data Protection PolicyThe University of Manchester Data Protection Policy

8. Author of this Data Management Plan (Name) and, if different to that of the Principal Investigator, their telephone & email contact details

[name]

[contact]

14.6 Participant Booklet

Getting help

If you have problems with the test kit, app, or answering the questions please get in touch so that we can help. To do this

- · Pop in to see us next time you're in hospital. We're in the new bit of the clinical trials unit. Go up ramp next to reception, turn right, we're next to the mosaic.
- Contact support: [contact]. This email is checked 9-5 throughout the working week.

The Christie Hotline

It is essential that you continue to contact your medical team as normal if you have any concerns about your health.

If you feel unwell, do not delay, call the Christie Hotline Immediately

[name]

Thank you

Kidney monitoring research How to take a reading at home

What we're doing

People with partly-working kidneys often don't get the choice of taking part in cancer trials because of worries over damaging their kidneys further. This means that there are fewer treatment options for people who have both cancer and kidney disease.

We want to understand whether people monitoring their kidneys at home via a simple blood test could help with this. Can it improve the understanding of what's happening with their kidneys and support they're given? If so, then this may eventually allow patients with partly-working kidneys to take part in cancer trials to improve treatment options of the future?

What you'll be asked to do

On Mondays, Wednesdays and Friday mornings for the next 8 weeks we would like you to check your kidneys by taking a 'creatinine reading' with the meter provided. Then send us the result using an app on your smart phone (designed for securely sending information). We'd also like to hear your feedback on the whole process at set points throughout the 8 weeks and through an informal interview at the end of the study.

This booklet aims to walk you through the use of the kidney monitoring kit and how to send your information in.

First: Testing the device itself

Take the test strips and bottles out of the fridge so that they are at room temperature before starting. Then wash your hands.

[figure not shown]
Step A: Put a new test strip in your meter. Press the left and right buttons until the screen says C1 as shown.

Everyone's creatinine result will be slightly different depending on your age, sex, race, muscle mass and even what you have eaten. When you start the study, we will give you an idea of what your baseline kidney function is. This will vary day to day, and it is completely normal for some variation in the results. Most people will have results between 60 and 120.

What do I do if the device screen goes blank?

The device times out after a minute, putting in a test strip or pressing a button on the device will wake it up again.

There is an error code on the device – what do I do?

If this happens please have a look in the device info leaflet. If this doesn't give you the answer, please let us know on the contact details provided. You do not need to change the battery of your device. If you have concerns with how your device is working, please contact us on [contact].

Why are the readings being checked Monday/Wednesday/Friday?

Ideally the home tests would be done every 2 days, however, people are only in the hospital to review them Monday to Friday. Therefore, for purely practical reasons, we chose to do the readings Monday, Wednesday, and Friday each week rather than asking people to do more.

What do I do if I lose or break my phone? What if the battery dies when I have taken a reading?

If you lose or break your phone, then let us know when you are able to. If you have taken a reading and your battery dies, please send us the reading as soon as you can when your phone is up and running again (even if it's just the number value and you didn't manage to get a photo of the reading at the same time).

I've missed a reading – what do I do?

If you miss a reading or can't do one on a particular day for whatever reason (e.g. travelling) please take a reading as soon as you can and send it in the normal way then go back to the usual schedule afterwards (Monday/Wednesday/Friday). The reading will still be very useful for us. If you don't have very good network and can't send a reading in, then just try again later or the next day. You will receive confirmation when you're reading has been successfully sent, if you have not received this, please try again.

How often would they be reviewed by staff?

A member of the study team will check the results once a week. We will not contact you about the readings during the study. If you feel unwell or are concerned in any way you should contact your team at the Christie/GP in the normal way.

14.8 Interview Guide

Interview Guide

- 1. What are your overall impressions of the study?
- 2. What did you think of the device? Calibration?
- 3. How could the device be improved?
- 4. What did you think of the app?
- 5. How could the app be improved?
- 6. Did you feel that the testing was too frequent?
- 7. Did the testing become part of your routine or was it a chore?
- 8. What did you think of the readings? Did you trust the results? Worry about the results?
- 9. Any other feedback you would like to give?

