7.1 Qualitative assessments

In both Part A and Part B of the study, a questionnaire based on a previously validated tool²⁷ will be used to assess participants view of the monitoring device along with the process of sending in data to the secure cloud environment. This will occur as outlined above.

At the beginning and end of Part B of the study, a previously validated quality of life questionnaire will be completed²⁸.

Semi-structured, individual interviews will be performed at the end of the study period for both Part A and Part B of the study. Participants will be asked a series of open-ended questions relating to their experience of the process and all aspects of the study. An interview guide is included in the appendix. The questions will broadly assess the following parameters:

- · Overall impressions of the study
- Acceptability of StatSensor® (Part A) including calibration and operation
- · Feedback on app
- Adherence with measurements including calibration and appropriateness of frequency
- For Part A opinion on frequency of readings too many or too few
- Opinions on value of readings/trust of readings
- · Any other participant-initiated reflections or observations

All interviews should last no more than 1 hour and will take place in a private room in the hospital. Interviews will be recorded using a digital recorder and will be transcribed verbatim by the lead researcher. Recordings and transcripts will be stored in a secure environment at The Christie Hospital. The recording will be used for thematic analysis during data analysis.

At the end of Part B of the study, a clinician interview will take place, exploring:

- Overall impressions of the study
- Trust of results and future applications

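### The interview guide's only question on test frequency is closed and one-directional, whereas section 7.1 promises open questions and, for Part A, opinion in both directions

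*Protocol*

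**What the plan says.** Section 7.1 (Qualitative assessments) sets out the interviews for both parts: "Semi-structured, individual interviews will be performed at the end of the study period for both Part A and Part B of the study". On format it says: "Participants will be asked a series of open-ended questions relating to their experience of the process and all aspects of the study". It introduces its topic list with "The questions will broadly assess the following parameters". Two entries in that list bear on how often participants test. One carries no restriction to either part: "Adherence with measurements including calibration and appropriateness of frequency". The other is specific to Part A and names both directions: "For Part A opinion on frequency of readings too many or too few". The section then points to the instrument: "An interview guide is included in the appendix".

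That instrument, Appendix 14.8, is a list of nine questions that is not divided by study part. Number 6 is the only one about frequency: "Did you feel that the testing was too frequent".

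Table 2 (section 4) names questionnaire and interview among the outcome measures for the Part A primary objective, patient acceptance of intensive home monitoring.

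**The concern.** Section 7.1 makes two commitments on this topic: the questions are open, and in Part A the participant's view is sought in both directions. Question 6 as written keeps neither. It invites a yes or no, and the only complaint it offers is that there was too much testing.

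What is at stake is the content of the acceptability evidence. Frequency is what makes the monitoring intensive. Section 5.2 makes Part B conditional on the process being acceptable to patients, and Part B keeps the same three weekly readings, for 6 weeks instead of 4. Part A is therefore the natural place to learn whether that rhythm suits participants.

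Wanting more readings is a plausible answer. The participant question-and-answer text in the appendix says that testing every 2 days would be the ideal, which is 7/2 = 3.5 readings a week against the 3 scheduled. It explains that the weekday pattern was chosen for practical reasons.

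**Working it through.** No arithmetic decides this point, because it depends on no rate, effect size, power or sample size. The check sets section 7.1 beside the guide and then looks for any other item that covers the missing direction.

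1. **Format.** Section 7.1 specifies open-ended questions. Question 6 can be fully answered with one word. Questions 2, 4 and 8 of the same guide open by asking what the participant thought of something, so question 6 also departs from the style of its neighbours.

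2. **Direction.** Section 7.1 names two directions for Part A, an excess of readings and a shortage. Question 6 prompts for the excess only.

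3. **What each opinion yields if the question is answered as put:**

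| Participant's view | Plain answer to question 6 |
|---|---|
| Tested too often | Yes |
| About right | No |
| Not often enough | No |

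The last two views give the same reply, so the scripted question alone does not separate them.

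4. **Other places where the missing view could surface:**

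- Guide question 7 asks whether testing became routine or a chore. This is a forced choice about burden and does not concern the number of readings.
- Guide questions 1 (overall impressions) and 9 (any other feedback) are open, but they capture a wish for more readings only if the participant volunteers it.
- The usability questionnaire (Appendix 14.1) asks in item 1 about willingness to use the process often. No item asks whether the number of readings was too high or too low.

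No scripted item in either instrument asks about too few readings.

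5. **Where the answer feeds in.** In Table 2 the interview sits beside the questionnaire, expected versus actual readings, timing of samples, and values sent versus values stored on the device. Interview feedback also serves the Part A exploratory objective of improving the algorithm. The numbered progression factors in section 5.3 are recruitment rate and adherence to readings, so opinion on frequency is not among them. Sections 7.1 and 9 assign the interviews to thematic analysis, and no tabulated proportion of answers is planned.

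**The case against.** The strongest reply is that Appendix 14.8 is a guide and not a fixed-response form. The interviews are semi-structured, may last up to an hour, are transcribed verbatim and are analysed by theme. Nobody is held to yes or no, and the interviewer may probe. Section 7.1 itself tells the interviewer that both directions are of interest, and it asks only that topics be assessed broadly, which does not prescribe wording. It can also be argued that excess burden is the main threat to acceptance, and that a participant who wants more tests is not showing poor acceptance.

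Most of this stands, and it limits the consequence. A reader might infer that Part A cannot distinguish satisfied participants from those wanting more readings. The documents do not support that, because probing and the open questions leave a route to the answer. A reader might also put a size on the bias by noting that each of the 12 participants is 1/12, or about 8 percentage points. That has no basis here: no proportion of answers to question 6 is to be reported, and nothing in the protocol shows that anyone would be led to say yes.

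The mismatch itself is not answered. Leaving an interviewer to improvise a topic that section 7.1 names explicitly is weaker than scripting it, and makes the 12 interviews less comparable. The argument about burden explains why one direction matters more, but section 7.1 still assigns both.

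**Conclusion.** The point holds as a minor inconsistency between section 7.1 and Appendix 14.8. As scripted, the guide does not reliably elicit the view that readings were too few or separate it from the view that they were about right, and it may lean towards burden. Probing and questions 1 and 9 offset this only in part.

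The effect is confined to one of several measures of the Part A primary objective. No progression factor listed in section 5.3 and no statistical figure depends on it, and no numerical size can be attached. The conclusion assumes that interviewers broadly follow the printed guide. If every interviewer raised both directions unprompted, the practical loss would be small and only the inconsistency of the documents would remain.

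**What to change.** Before the first interview, replace question 6 of Appendix 14.8 with a neutral open question, for example: *How did you find the number of tests each week? Would you have preferred more, fewer, or the same, and why?* Analyse the answers within the thematic analysis already planned. Recording them additionally in three categories is optional and is not needed to resolve the mismatch.

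The cost is a one-line change to the appendix, documented as an amendment under section 10.7. It alters no schedule and adds no burden for participants.

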14.9 SAE Reporting Form

REPORT OF SERIOUS ADVERSE EVENT (SAE)

(For all studies except clinical trials of investigational medicinal products)

The Chief Investigator should report any SAE that is both related to the research procedures and is unexpected. Send the report to the Research Ethics Committee that gave a favourable opinion of the research within 15 days of the CI becoming aware of the event.

1. Details of Chief Investigator

Name:	
Address:	
Telephone:	
Email:	
Fax:	

2. Details of study

Full title of study:				
Name of main REC:				
Main REC reference number:				
Research sponsor:				
Sponsor's reference for this report:				
(if applicable)				
3. Type of event Please categorise this event, ticking all appropriate options:				
Death	Life	threatening		Hospitalisation or prolongation of existing hospitalization
Persistent or significant	Cor	ngenital anomaly		Other
disability or incapacity	or b	oirth defect		
4. Circumstances of event				
Date of SAE:				
Location:				
Describe the circumstances of the event:				
(Attach copy of detailed report if necessary)				
What is your assessment of the implications, if any, for the safety of study participants and how will these be addressed?				

5. Declaration				
Signature of Chief Investigator:				
Print name:				
Date of submission:				
6. Acknowledgement of receipt by main REC (please insert name):				
The [] Researc	th Ethics Committee acknowledges receipt of the above.			
Signed:				
Name:				
Position on REC:				
Date:				

Signed original to be sent back to Chief Investigator (or other person submitting report)

Copy to be kept for information by main REC.
